8.3.4 Adherence

The study team will monitor the use of Wysa and assure the system is being used within designed parameters during the study.

8.4 Data Collection

8.4.1 Randomisation

8.4.1.1 Sequence Generation

Demographic data will be collected from all patients immediately after they complete the informed consent process, during the same phone call. Together with data from the IAPT referral, this information will be used in the randomisation algorithm to ensure that the intervention and control groups are balanced on key variables (gender, age, ethnicity, self-reported antidepressant use, and severity of depression).

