6 STUDY FLOW CHART

This project will conduct a real-world evaluation of Wysa as an early intervention tool introduced into the mental health referral pathway for adult IAPT service. There is currently an average wait time for IAPT between referral and treatment start of 8+ weeks with 95% of people starting treatment within 18 weeks [1]. Wysa will be made available to patients upon referral to IAPT. The control group will continue with service as usual whilst the test group will interact with Wysa while waiting for treatment.

Wysa will remain available to patients throughout their progression through the standard clinical pathway. Patients will be provided with information about the study at their initial referral point and will be contacted by our research assistants to collect informed consent and provide the product link. This will enable Wysa to offer immediate support tools and monitoring. While patients are waiting for treatment, Wysa will serve as a screening support tool for flagging assessment needs to the clinical team. After patients have received treatment, Wysa can be used as an extended monitoring tool. This is in line with the IAPT manual 2018's future goal [2] of using an app to prompt patients to fill in key outcome measures at regular intervals during the follow-up year, providing patients with easy access to their relapse prevention plan, alerting the service if relapse has occurred, and facilitating the scheduling of booster sessions. Figure 1 demonstrates the current clinical IAPT pathway with the proposed study procedures in blue.

[figure not shown]

Figure 1. Current clinical pathway for adult IAPT referral and proposed study procedures (blue) (adapted from [2])

Based on the artificial intelligence (AI) recommendations generated by Wysa, patients may be passed to the IAPT for a full assessment using a combination of outcome measure scores and language used within the tool. A copy of the patients' responses to outcome measures will be

automatically pushed into their electronic patient record through the Mayden clinical information system and an automated email will be sent to the referrals coordinator to flag the need for onward referral.

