Two questionnaires will be used to assess health-related quality of life: the EQ-5D-5L [40] and the Short Form 12 (SF-12) health survey [41]. The EQ-5D-5L provides a descriptive self-assessment of health in 5 dimensions: mobility, self-care, usual activities, pain/discomfort and anxiety/depression [40]. It is commonly used as a quality of life measure to conduct cost effectiveness analyses [42]. The EQ-5D-5L has a greater emphasis on physical than mental health, but has demonstrated the ability to capture changing anxiety severity [43]. The SF-12 survey is a reliable measure of functional health and is well-suited for this study, as it includes mental health items and has been shown to be acceptable for use as a screening tool for depressive disorders [44].

Cost-effectiveness

To conduct a health economic analysis, the study will collect data on health and social care service use, medication use and treatment costs, the implementation costs of Wysa, out of pocket medical expenses borne by patient and carers and productivity related costs such as work absence / time off work due illness. This data will be combined with the quality-of-life indicators to produce an assessment of the costs of adopting Wysa from the perspective of both the UK health and social care services and the wider society [45]. This analysis will also produce a budget impact model for each site that will be used to provide a final overall implementation strategy for more rapid adoption at other NHS sites and dissemination across the AHSN network in partnership with the new Integrated Care Systems. The team will also incorporate the environmental sustainability calculation in line with the Greener NHS agenda.

Table 6. Secondary Outcome Measurement

Secondary Outcome	Outcome Measure
Anxiety severity	
 Score on the GAD-7 [37]
Crisis identification	
 Number of users identified by the app for escalation of care compared to the number of patients in the control group who access A&E or out-of-hours services while waiting for treatment
Engagement	
 Uptake rates Dropout / 'did not attend' rates App usage data Qualitative feedback from semi-structured interviews
Acceptability	
 Qualitative feedback from semi-structured interviews Automated review questions periodically requested during general use of the tool

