8.3.2 Sampling

8.3.2.1 Sample Size

Approx 1100 eligible patients are seen per month at the IAPT in the CNWL NHS Foundation Trust. Preliminary work suggests that Wysa is associated with a mean clinical improvement in PHQ-9 of 5.84 (SD6.66) [28]. This study is powered to detect a clinically meaningful effect on the PHQ-9 scale [28]. Based on a SD of 6.6 and a 2:1 recruitment ratio (usual care: intervention) a sample size of 393 would allow detection of a difference in PHQ-9 of at least 2 points, with 80% power. Augmenting the sample size to 480 would allow for 20% attrition, whilst still maintaining sufficient power to detect clinically and statistically meaningful differences with a Type 1 error rate of 0.05. This inflated sample size would also allow for adjustment for stratification variables, gender, age, ethnicity, self-reported antidepressant use, and severity of depression.

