8.3.3 Recruitment

8.3.3.1 Participant Identification

Participants who are referred, or refer themselves, to IAPT for mental health support (online or by phone) will be recruited from the three provider sites of the London Community Living Well Service, run by the Central North West London NHS Foundation Trust. The service receives on average 1100 referrals a month. All referrals will be screened by the psychology assistant against exclusion criteria and those eligible for the trial will be provided with information regarding the trial via email (see 13.1 Appendix 1). The psychology assistant will then contact participants to check further exclusion criteria not clear from service referral and to take informed consent. Screening will continue through the first 6 months of the intervention period, and we expect to be able to onboard significantly more individuals than our target sample size. All participants will have access to the Wysa app (including control participants who will receive access following the control period).

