8.5 Data Analysis

8.5.1 Statistical Methods for Primary Outcome

Descriptive statistics will be used to characterise users, assess baseline comparability, and compare side effects. Primary comparisons between intervention and control groups will be conducted for primary and secondary outcomes. Primary analyses are designed with 80% power to detect a two-sided α of 0.05. All analyses will report 95% CI around estimate of effect. Comparative analyses will be conducted on an intention to treat basis, using linear or logistic regression, with adjustment for stratification variables.

We will explore missingness in our data, be that in relation to primary outcomes, follow-up data and in WYSA analytic information. The proportion of missing data will be explored and reported on descriptively. An hypothesised scenario, where patients remove themselves from the waiting list for treatment before the duration of follow-up may lead to missing data scenario. Currently, estimates

suggest that xxx% of our cohort will 'drop-off' waiting list before our primary endpoint. We will conduct exploratory sensitivity analyses in a complete case ('per protocol') cohort compared with the ITT analysis.

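### Site is missing from the planned adjustment variables although three sites recruit; adding it as a fixed effect would give a small, nearly free gain in precision

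*Protocol*

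**What the plan says.** Protocol 8.3.3.1 states that participants "will be recruited from the three provider sites of the London Community Living Well Service", all run by one NHS Trust. Sections 5 and 8.4.1.3 also give three sites.

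Protocol 8.4.1.1 lists the factors used in allocation, so that "intervention and control groups are balanced on key variables (gender, age, ethnicity, self-reported antidepressant use, and severity of depression". The SAP repeats the five. Protocol 8.3.2.1 names the same five when it says that the inflated sample leaves room for adjustment.

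Protocol 8.5.1 plans the comparisons "using linear or logistic regression, with adjustment for stratification variables". Read with 8.3.2.1, this means the five patient characteristics. The SAP describes linear regression of PHQ-9 and GAD-7 to compare the arms and names no covariate.

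Protocol 8.5.2 allows secondary analyses to adjust further for factors that look imbalanced at baseline. Site is not named there either.

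The one output promised by site is economic: "This analysis will also produce a budget impact model for each site" (8.2.5.2, repeated in 10.1).

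**The concern.** Site is fixed before randomisation and cannot be affected by treatment. Where several sites recruit, outcomes may differ between them through local case mix, staffing or service delivery. If site is not in the model, that variation is counted as unexplained noise and the confidence interval for the PHQ-9 difference is slightly wider than it needs to be.

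The sample has little slack. The protocol asks for 393 evaluable participants, but 480 less 20% leaves 384, and section 9.8 itself describes the sample as close to the minimum for adequate power. A covariate that is probably already held and costs almost nothing is worth using.

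**Working it through.** **Inputs from the documents**
- Significance level and power: "Primary analyses are designed with 80% power to detect a two-sided α of 0.05" (8.5.1).
- Target: "detection of a difference in PHQ-9 of at least 2 points, with 80% power" (8.3.2.1).
- Spread and ratio: "Based on a SD of 6.6 and a 2:1 recruitment ratio (usual care: intervention" (8.3.2.1). The same section gives the preliminary SD as 6.66.
- Stated sample: 393 evaluable, 480 recruited, 20% attrition.

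**Assumed input.** The between-site share of PHQ-9 variance, ρ, is not in the documents. I take 1% to 5%, meaning variance that the five existing covariates do not already explain.

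**Step 1: reproduce the plan's figure.** With 2:1 allocation, total N = 4.5 × [SD × (1.960 + 0.842) / 2]².
- SD 6.6: 384.6. Rounding the larger arm up gives 257 + 128.5, or 386.
- SD 6.66: 262 + 131 = 393, which matches exactly.

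The stated figure therefore reproduces, apparently from the unrounded SD. The SAP puts the larger arm on intervention and the protocol puts it on usual care. With equal variances this does not alter N or power.

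**Step 2: power as planned, without site.** Completers = 480 × 0.8 = 384, split 256 and 128.
- SE = 6.6 × √(1/256 + 1/128) = 0.714.
- Power = Φ(2/0.714 − 1.960) = 79.9%.

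**Step 3: power with site in the model.** If 6.6 is the total SD, the residual SD becomes 6.6 × √(1 − ρ). The equivalent number of extra completers is 384/(1 − ρ) − 384.

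| ρ (assumed) | Residual SD | Power at 384 | N needed | Equivalent extra completers |
|---|---|---|---|---|
| 0 | 6.600 | 79.9% | 386 | 0 |
| 1% | 6.567 | 80.3% | 381 | 4 |
| 2% | 6.534 | 80.7% | 378 | 8 |
| 5% | 6.433 | 81.9% | 366 | 20 |

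**Step 4: the other reading of the SD.** If 6.6 were a within-site SD, the total SD would be 6.6/√(1 − ρ). Leaving site out would then lower power from 79.9% to 79.5%, 79.1% and 77.9% at 1%, 2% and 5%. The documents do not say which reading applies.

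**Step 5: what these shares mean in points.** The between-site SD is 6.6 × √ρ: 0.66 at 1% and 1.48 at 5%. For three equal, evenly spaced sites, the gap from lowest to highest mean is 2 × √1.5 times that SD: about 1.6 points at 1% and 3.6 at 5%. The upper end is generous beside a target effect of 2 points.

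**Step 6: bias and type I error.** A simulation used three equal sites, 384 participants, 2:1 allocation that ignored site, shares from 0% to 10%, and 8,000 runs per scenario. With site left out of the model:
- a true difference of 2 was estimated at 2.00 to 2.01 on average;
- the rejection rate under no effect was 4.9% to 5.2%.

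With no site differences, adding site changed simulated power from 79.8% to 79.5%. That is the whole price of the 2 degrees of freedom.

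**The case against.** The strongest reply is that nothing is invalid. The plan adjusts for the variables it balances on, which is coherent. If 6.6 is a total SD, the stated power already absorbs any site variance. The three sites belong to one service in one Trust, and the five covariates would pick up part of any difference in case mix, so the true gain may sit at or below the low end. All of this stands. It limits the point to a modest gain in precision but gives no reason to leave site out.

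Several stronger readings are tempting, and the documents do not support them:

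- **The effect estimate is biased or the test too liberal.** Individual randomisation rules this out, and the simulation agrees.
- **Waits differ by site, so treatment exposure at three months differs by site.** The protocol gives one overall figure, "average wait time for IAPT between referral and treatment start of 8+ weeks with 95% of people starting treatment within 18 weeks", and none by site.
- **Clinical results are promised by site.** Only a budget impact model is promised. Nothing says that it uses arm proportions within a site, so chance imbalance there is not shown to harm it.
- **Site is shut out of every model.** Protocol 8.5.2 could admit it in secondary analyses if it looked imbalanced. That is still a data-driven route and does not pre-specify site.
- **The randomisation algorithm should be changed.** The SAP, dated 8 August 2023, describes randomisation in the past tense, so a change would come too late.

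The SAP also reports the regressions as already done. Altering the primary model after seeing outcomes would be post hoc, and the fix has to respect that.

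**Conclusion.** The point holds as one about precision. Site is not pre-specified in the allocation factors or in any model whose covariates are named, so between-site variation in PHQ-9 stays in the residual. For an assumed 1% to 5% share, adjustment is worth about 0.4 to 2 percentage points of power at 384 completers. With no site differences the loss is negligible.

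This rests on 6.6 being the total SD, on 20% attrition, and on a site share that the documents do not supply. It also assumes that each participant's site is recorded, which a budget model by site implies but which the documents do not state.

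**What to change.** - In Protocol 8.5.1 and the SAP, add site (three levels) as a fixed effect beside gender, age, ethnicity, antidepressant use and depression severity. Do this in the PHQ-9 and GAD-7 models, and in the EQ-5D-5L, SF-12 and cost models. Name these covariates in the SAP, which at present lists none.
- If outcome data have already been analysed, leave the primary model as it was and report the site-adjusted result as a labelled sensitivity analysis.
- Define site once. Section 9.4.2 speaks of two sites and 9.5 refers to both clinical sites, against three elsewhere. The first may mean partner locations for public involvement, but the text does not say so. State also which sites the budget model covers.

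The cost is a line or two in the SAP and 2 degrees of freedom out of about 380. No new data collection should be needed, and no change to the randomisation algorithm is proposed.

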8.4.1.2 Allocation Concealment Mechanism

Consenting participants will be inputted into a masked computer randomisation algorithm and the outcome will be recorded in an electronic record to conceal treatment allocation from study researchers. Participants will be sent an automatic email to inform them of their group assignment, and participants in the intervention group will receive the link to download Wysa.

8.4.1.3 Implementation

Psychology Assistant recruited specifically for the trial and covering the three London Community Living Well Service sites will enrol participants in the study. A computer will generate the random allocation sequence and assign participants to interventions.

8.4.2 Blinding

Due to the nature of the intervention, no blinding of participants will be possible in the study, as all participants will know whether or not they are using the app. Clinical treatment teams will also not be blinded as they will know through the electronic patient record if a participant has received the intervention. The evaluation team will be blinded to treatment using the randomisation algorithm.

8.4.3 Methods of Data Collection

The timeline for the data collection is detailed in Figure 5.

[figure not shown]

Figure 5. Data collection sequence diagram

8.4.3.1 Quantitative data collection

The quantitative outcome measures will be delivered directly to patients through the Wysa app or by Qualtrics survey (e.g. for participants in the control group). Participants in both conditions will complete four questionnaires at baseline and 3-months post-randomisation (PHQ-9, GAD-7, EQ-5D-5L, and SF-12). Outcome measures have been chosen that will not be a significant burden for participants to complete; none of the questionnaires are longer than 12 items or expected to take more than a few minutes each to complete. Together, the questionnaires should take participants from 10 to 20 minutes to complete. Patient responses will be automatically uploaded to the iaptus electronic patient records using the Mayden Prism API. App use data will be automatically stored through the app.

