7.2 Rationale

A key issue with the current mental health service provision is lack of accessibility. Our solution enables immediate service provision at the point of referral, to mitigate the impact of long wait times to access mental health services. Onboarding processes at the point of referral to IAPT involve collecting routine outcome measures (aligned to existing service referral measures). Users are asked to provide information and goals to personalise the guided self-help or escalation recommendations. These are provided using a combination of AI-enabled self help tools, natural language processing and conversation engines. Our Application Programming Interface (API) through the Mayden Prism system then pushes data directly into the iaptus electronic patient records and automates safety alerts.

Our preliminary work suggests that implementing Wysa's self help tools at the onboarding stage will result in improved outcomes for the service user, whilst automations in the referral process will result in less assessments that are then screened out of the service and a more comprehensive risk identification whilst awaiting assessment [28]. This is based upon our previous findings from our 2018 study showing a significant decrease in depressive symptoms in users of Wysa versus non users [28].

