8.2.3 Intervention(s)

Wysa is a guided self-help and triaging tool delivered to patients via an app or widget. It uses Natural Language Processing to understand individuals' written inputs but not to generate responses. Wysa makes use of a wide range of clinically underpinned modules whilst gamification, clinical outcome measures and AI promotes engagement, improving efficacy and triage and reducing the cost of scale.

Wysa is delivered as a standalone system which patients download directly onto their personal device. Upon self-referral or professional referral to IAPT services the individual is automatically sent

a download link via sms or email. Once downloaded, data from within the app, including outcome measures, tools used and crisis alerts are automatically pushed to the electronic patient record iaptus using the Mayden Prism software. When considering the application of AI to mental wellbeing, the ability to feel listened to is the most influential factor in patient satisfaction and response. Users need to feel able to share their thoughts with the AI and our user testimonials show that the anonymous nature of this text-based interaction is imperative to them, even though they know they are communicating with an AI. Wysa has benefited from over 6 million conversations around the world to build up a complex listening algorithm, rules engine and content library. Clinical safety is applied to our rules engine and Content library to ensure that we regularly test for appropriateness, empathy, and presence of triggers in cases of misdirection. Each of Wysa's AI models is validated on at least 10,000 records that are manually tagged and not a part of the training set. Overall, Wysa has 100 million conversations to draw upon, with over 2 million users globally, which helps us overcome the cold-start problem that most AI faces.

Wysa can be used as a native app through android or IOS or as a web widget.

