8.3.1.2 Exclusion Criteria

- Patients ineligible for the standard IAPT care pathway;
- Patients with previous and current known major mental illness such as Schizophrenia, severe depression, any co-morbid neurological or neuro-psychiatric condition such as epilepsy;
- Patients with current psychosis or a history of psychotic symptoms within the last 6 months
- Patients with suicidal ideation;
- Patients scoring > 15 points on PHQ- 9;
- Patients scoring > 15 points on GAD- 7;
- Patients with significant cognitive disorders;
- Patients with noted neurodevelopmental conditions such as autism or ADHD;
- Patients previously diagnosed with a personality disorder;
- Patients who been under the care of CMHT or a specialised mental health services in the last 2 years;
- Patients who failed IAPT previously;

- Patients with referrals for specialist presentations of pre-existing, diagnosed conditions requiring a specialised assessment beyond the standard clinical pathway;
- Incapable of self-consent;
- In a dependent/unequal relationship with the research or care teams or any PPI representatives.

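### Baseline questionnaires are not placed before randomisation, and any baseline taken in the app would follow allocation, in the intervention arm only

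*Protocol*

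**What the plan says.** - **Assessments.** Protocol 8.4.3.1: "Participants in both conditions will complete four questionnaires at baseline and 3-months post-randomisation". The four are PHQ-9, GAD-7, EQ-5D-5L and SF-12. They are "delivered directly to patients through the Wysa app or by Qualtrics survey (e.g. for participants in the control group"). Protocol 8.2.5.1, 8.2.5.2 and 9.1 also describe PHQ-9 and GAD-7 as reaching patients through the app.
- **Before allocation.** Protocol 8.3.2.2 puts allocation after consent and demographic information. Protocol 8.4.1.1 collects the demographic data on the consent call and adds: "Together with data from the IAPT referral, this information will be used in the randomisation algorithm". Severity of depression is one of the balancing variables.
- **At allocation.** Protocol 8.4.1.2 sends an automatic email naming the arm, and "participants in the intervention group will receive the link to download Wysa". The SAP repeats this.
- **A different account of the link.** Protocol 8.2.3 has each person sent "a download link via sms or email" automatically on referral. Section 6 has research assistants supply it when they take consent. Section 8.3.3.1 and the GP letter (Appendix 4) give controls the app only after the control period of 3 months.
- **Earlier scores.** Protocol 8.3.1.2 excludes "Patients scoring > 15 points on PHQ- 9", with the same limit on GAD-7. Protocol 7.2 says: "Onboarding processes at the point of referral to IAPT involve collecting routine outcome measures".
- **Use of baseline.** Protocol 8.5.1 adjusts for the stratification variables, and 8.5.2 plans exploratory analyses by depression severity. The SAP uses baseline for comparability and for post hoc regressions in subsets with a low baseline PHQ2. It does not say when baseline is taken or from which source.

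**The concern.** A baseline should be fixed before anyone knows the arm. Here the primary outcome is self-reported and participants are not blinded (Protocol 8.4.2). If the intervention arm gives its baseline inside the app, those answers come from people who know they were given Wysa and have already opened it. Controls would answer a survey link, possibly knowing that they were not given it.

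Two things would follow. First, any table, subgroup or covariate built on that score would condition on something allocation may already have changed. Second, whether a baseline exists at all would depend on downloading the app, in one arm only. EQ-5D-5L and SF-12 are the most exposed, because no earlier source is described for them, and Protocol 8.2.5.2 combines quality-of-life data with costs in the economic analysis.

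**Working it through.** The point concerns timing, and the plan gives no figure for it. I set the passages in order and then size the consequence under stated assumptions.

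**1. Order of events in the text.** Consent and demographic data on one call (8.3.2.2, 8.4.1.1); randomisation; email naming the arm, with the app link for the intervention arm (8.4.1.2); questionnaires by app or Qualtrics (8.4.3.1). A baseline answered in the app therefore comes after randomisation, disclosure and download. A baseline answered in Qualtrics could come before or after; the text does not say.

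**2. Does the other account of the link change this?** If 8.2.3 applied as written, the link would go out on referral, before consent, to future controls as well. That conflicts with 8.4.1.2, with 8.3.3.1 and with Appendix 4. Section 6 gives a third timing. These passages must be reconciled; none of them states that the four questionnaires are completed before allocation.

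**3. Which scores must predate allocation?**

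| Measure | Source before randomisation described? |
|---|---|
| PHQ-9 | Yes: exclusion limit (8.3.1.2); depression severity also enters the algorithm (8.4.1.1) |
| GAD-7 | Yes: exclusion limit (8.3.1.2) |
| EQ-5D-5L | None |
| SF-12 | None |

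PHQ-9 and GAD-7 may therefore have two candidate baselines each, and neither document chooses between them.

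**4. Which analyses are touched?**
- An unadjusted comparison of 3-month PHQ-9 uses no baseline and is untouched.
- A comparison adjusted for the severity variable used in randomisation (8.5.1) uses a score that predates allocation and is largely protected.
- Baseline comparability tables, severity subgroups, and any model using an app-onboarding score are exposed.
- Any EQ-5D-5L or SF-12 analysis that uses its own baseline is exposed.

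**5. Size of bias if a post-allocation score is the covariate.** Let *s* be the amount by which the intervention baseline has already fallen relative to control, and *b* the regression slope on baseline. With a true difference of 2 points (the target in 8.3.2.1 and the SAP):

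adjusted estimate = 2 − *b* × *s*; bias = *b* × *s*

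Both *b* and *s* are assumed; the documents give neither.

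| *b* | *s* = 0.5 | *s* = 1.0 |
|---|---|---|
| 0.3 | bias 0.15, estimate 1.85 | bias 0.30, estimate 1.70 |
| 0.5 | bias 0.25, estimate 1.75 | bias 0.50, estimate 1.50 |
| 0.7 | bias 0.35, estimate 1.65 | bias 0.70, estimate 1.30 |

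At *b* = 0.5 the bias is 0.25/2 = 12.5% to 0.5/2 = 25% of the target difference. A shift in the other direction would reverse the sign.

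**6. Availability.** The intervention arm is 480/3 = 160 under the protocol's ratio, or 320 under the SAP's, which reverses it. If 10% to 30% do not download promptly (assumed), 16 to 48 of 160, or 32 to 96 of 320, would have a late or missing app baseline.

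**The case against.** The strongest reply is that nothing here proves a post-randomisation baseline.

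- The control group is only an example in 8.4.3.1, so Qualtrics is open to the intervention arm too. *This stands.*
- Figure 5 holds the data collection timeline and Figure 4 the participant flow. Neither is shown, and either may settle the order. *This stands.*
- Protocol 7.2 ties routine measures to the point of referral, which fits a PHQ-9 and GAD-7 taken before randomisation at least as well as it fits app onboarding. *This stands, for those two measures.*
- The severity covariate must exist before it can feed the randomisation algorithm. *This stands, and it protects the adjusted primary estimate.*

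A reader might infer that the intervention baseline can only follow allocation. The first two replies show that the text does not go that far. A reader might also infer a bias of the full 0.5 to 1.0 point. That would need a change-score analysis, and none is planned: the outcome is the PHQ-9 score, analysed by regression. Nor does a late baseline move the endpoint, since follow-up is fixed at 3 months from randomisation. A later score above 15 would not by itself undo eligibility, because screening precedes allocation.

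What the reply does not meet: no supplied text puts the four questionnaires before allocation, neither document names the analysis baseline, several sections describe app delivery, and EQ-5D-5L and SF-12 have no described earlier source.

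**Conclusion.** The concern holds as a conditional weakness. As the text reads, any app-delivered baseline follows randomisation, disclosure of arm and download in one arm only, and depends on uptake. The text leaves open whether baseline is in fact taken that way, and the missing figures may answer it.

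The adjusted primary PHQ-9 estimate is largely safe, provided that the severity covariate is the one used in randomisation. The exposure is to baseline comparability tables, severity subgroups, any adjustment using app-onboarding scores, and EQ-5D-5L and SF-12. The post hoc PHQ2 subsets in the SAP could be affected as well, but the source of that score is not given.

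The 0.25 to 0.5 point figure is illustrative. It rests on an assumed slope of 0.5 and an assumed shift of 0.5 to 1.0 point, and it applies only if a post-allocation score is the covariate. It is not an estimate of bias in this trial. The case for acting rests on the better method being cheap.

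**What to change.** **For enrolment still to come.** In Protocol 8.4.1.1 and 8.4.3.1, have every participant complete all four questionnaires by the same Qualtrics link after consent. Randomise, and release the allocation email, only once they are submitted. Reconcile section 6, 8.2.3 and 8.4.1.2 on when the app link is sent, and check Figures 4 and 5 against the result.

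**For participants already randomised.** The SAP, dated 8 August 2023, describes randomisation in the past tense, so this part may matter most.
- In the SAP, define baseline PHQ-9 and GAD-7 in both arms as the last score recorded before the randomisation timestamp. Do not use app-onboarding scores as baseline covariates or to define subgroups.
- For EQ-5D-5L and SF-12, report by arm when baseline was taken relative to allocation. Add a sensitivity analysis that does not use a post-allocation baseline, for example 3-month scores adjusted for the randomisation variables only.

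**Cost.** The first part needs an amendment that reorders an existing survey and email. A few people who consent but do not complete the survey would not be randomised, and allocation would be slightly delayed. The second part needs SAP wording and the screening scores, assuming that they were stored as dated values. It cannot recover a pre-allocation EQ-5D-5L or SF-12 where none was taken.
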